5.2 DEFINITION OF SERIOUS ADVERSE EVENT

A serious adverse event (SAE) is defined as an adverse event that:

- Led to death
- Led to serious deterioration in the health of the patient that resulted in:
 - o A life-threatening illness or injury
 - o A permanent impairment of a body function
 - In-patient or prolonged hospitalization
 - Medical or surgical intervention to prevent life-threatening illness or injury or permanent impairment to body structure or a body function

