5.3 ADVERSE EVENT ASSESSMENT AND DOCUMENTATION

All subjects who have been exposed to the study treatment shall be evaluated for adverse events. All adverse events, regardless of severity and whether or not they are ascribed to the study treatment, shall be recorded in the source documents and CRF using standard medical terminology.

All adverse events shall be evaluated beginning with onset, and evaluation shall continue until resolution is noted, or until the investigator determines that the subject's condition is stable. The investigator shall take appropriate and necessary therapeutic measures required for resolution of the adverse event. Any medication necessary for the treatment of an adverse event must be recorded on the adverse event case report form.

All AEs shall be characterized by the following criteria:

Page 32 of 65

- Event diagnosis
- Intensity or severity
- Expectedness
- Relatedness to study treatment
- Treatment or action taken.
- Outcome

Whenever possible, recognized medical terms should be used when recording AEs. Colloquialisms and/or abbreviations should not be used. Only one medical concept, preferably a diagnosis instead of individual symptoms, shall be recorded as the event.

If more than one distinct adverse event occurs, each event shall be recorded separately.

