5.3.5 Outcome

The clinical outcome of an AE shall be characterized as follows:

- Resolved without sequelae
- Resolved with sequelae (specify)
- Ongoing (i.e. continuing at time of study discontinuation)
- Death
- Unknown

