5.5 SERIOUS ADVERSE EVENT AND UNANTICIPATED ADVERSE DEVICE EFFECT REPORTING

SAEs and unanticipated adverse device effects (UADE) must be reported to the study sponsor (Tear Film Innovations, Inc.) and study Principal Investigator (PI) as soon as possible and no later than **24 hours** after the investigator first learns of the event.

For initial reports, Investigators shall record all case details that can be gathered within the reporting timeframe. The contact information for Tear Film Innovations, Inc. and the PI is below:

Study Sponsor:

Relevant follow-up information shall be submitted to the sponsor as soon as it becomes available and/or upon request. For some events, the sponsor or his designee may follow up with the site by telephone, fax, electronic mail, and/or a monitoring visit to obtain additional case details deemed necessary to appropriately evaluate the event (e.g., hospital discharge summary, consultant report, or autopsy report). Reports relating to the subject's subsequent medical course must be submitted to the study sponsor until the event has subsided or, in case of permanent impairment, until the event stabilizes and the overall clinical outcome has been ascertained.

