Were you able to remove the disposable from the packaging and load the disposable into the device as instructed by the User's manual?	☐ Yes ☐ No		
Were you able to apply pressure to the eyelid without difficulty?	☐ Yes ☐ No		
Were you able to apply heat to the eyelid without difficulty?	☐ Yes ☐ No		
Were you able to view the eyelid margin with the magnifier without difficulty?	☐ Yes ☐ No		
Were you able to recharge the battery as described in the User's manual?	☐ Yes ☐ No		
For an answer of "No" above, please provide additional details below:			

FORM 8: ADVERSE EVENT- Page 1 of 1

Timepoint of adverse event:	☐ Treatment ☐ Post-Treatment ☐ Follow-Up☐ No Adverse Events for this Subject
Date adverse event began (DD-MMM-YYYY)	
Time adverse event began (24-hour format, HH:MM)	:
Was the event a serious adverse event (SAE)? If Yes, indicate which criteria meets the protocol definition of SAE Led to death Led to serious deterioration in the health of the patient that resulted in: - A life-threatening illness or injury - A permanent impairment of a body function - In-patient or prolonged hospitalization - Medical or surgical intervention to prevent life-threatening illness or injury or permanent impairment to body structure or a body function Was the event device-related? Was the event procedure-related? Was the event an unanticipated adverse event?	☐ Yes ☐ No ☐ Related ☐ Not Related ☐ Related ☐ Not Related ☐ Yes ☐ No
Event severity	☐ Mild ☐ Moderate ☐ Severe
Diagnosis of adverse event:	
Treatment or action taken to treat adverse event:	□ None □ OTC/Rx Drug □ Non-Drug Treatment/Procedure □ Hospitalization/ER Visit
Action taken during procedure:	☐ None ☐ Study Procedure Interrupted ☐ Study Procedure Discontinued
Outcome of event:	☐ Resolved without sequelae ☐ Resolved with sequelae (specify below) ☐ Ongoing ☐ Death ☐ Unknown
Date of resolution:	Time of resolution:: □ N/A
Briefly describe the event, including any sequelae:	
Investigator Signature:	Date:Page 52 of 65

SUBJECT ID:	_
-------------	---

FORM 9: DEVI	CE EXPERIENCE REPO	RT FORM- Page I of I
Date of event (DD-MMM-YYYY)		
Time of event (24-hour format, HH:MM)	:	-
Did the event result in an adverse event?	☐ Yes ☐ No	If Yes,please fill out an AE Form
Device(s) involved in the event (check all that apply):	☐ iLux Instrument ☐ iLux ☐ QC Checkor ☐ Magnifie	Disposable ☐ Batteries ☐ Charging Stand
	☐ Other, please specify:	

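### The SAE definition leaves out permanent structural damage that occurs without functional loss, although intervention to prevent the same damage can make an event serious

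*Combined protocol and SAP*

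**What the plan says.** Section 5.2 makes an adverse event serious if it led to death or if it "Led to serious deterioration in the health of the patient that resulted in" one of four things. Two of the four matter here:

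- the impairment item: "A permanent impairment of a body function";
- the intervention item: "Medical or surgical intervention to prevent life-threatening illness or injury or permanent impairment to body structure or a body function".

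Form 8 in the Case Report Forms appendix carries the same list. Its impairment item also names function alone, and its intervention item also ends with "permanent impairment to body structure or a body function". The form tells the site to "indicate which criteria meets the protocol definition of SAE" and offers no 'other' category.

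The classification has consequences elsewhere in the plan:

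- Section 2.3 lists AEs and SAEs as the safety outcome measures.
- Section 7.3 summarises them by number and percentage of subjects.
- Section 5.5 begins "SAEs and unanticipated adverse device effects (UADE) must be reported to the study sponsor" and sets a 24-hour limit.

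**The concern.** Two items in one list treat body structure differently. Where structural damage is averted by intervention, structure is recognised as a reason for seriousness. Where the damage happens and stays, it is not, unless function is lost too. Nothing in the documents suggests that this was intended, and the intervention item shows that the sponsor regards structure as relevant.

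The gap is relevant to this study. The device heats and compresses the lid (section 1.2). Its disposable may touch the conjunctiva or cornea (section 5.4.1). The objective is to measure corneal and surrounding tissue temperature straight after heating (section 2.1). Lasting structural injury to the lid or cornea is therefore a kind of harm that a safety definition here should be able to classify. If such an event fell in the gap, it would be missing from the SAE count, and section 5.5 would not require a 24-hour report of it as an SAE.

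**Working it through.** The plan states no figure on this point, so the check is a reading of the criteria side by side.

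**Step 1: what each item names.** The two sources agree, so a text-extraction fault in one place does not explain the difference. Every cell applies only if the event also counts as serious deterioration in health.

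| Situation | Function | Structure |
|---|---|---|
| Intervention to prevent permanent impairment | named (5.2, Form 8) | named (5.2, Form 8) |
| Permanent impairment that has occurred | named (5.2, Form 8) | not named in either |

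Three of the four cells can lead to an SAE. The fourth cannot do so by itself.

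**Step 2: a test case.** Take an event judged to be a serious deterioration in health that leaves a permanent lid-margin or corneal scar, with no permanent functional loss and no intervention.

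| Criterion | Met? |
|---|---|
| Death | No |
| Life-threatening illness or injury | No |
| Permanent impairment of function | No, by construction |
| Hospitalization | No |
| Intervention to prevent impairment | No, none was made |

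No criterion is met, so the event is not an SAE. Change one feature and the answer can change. If the scar permanently reduces vision, the function item can apply. If someone intervened to prevent permanent structural damage, the intervention item can apply.

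**Step 3: does other text close the gap?**

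- *Definition.* No other section in the supplied text widens it.
- *AE recording.* Section 5.3 says "All adverse events, regardless of severity and whether or not they are ascribed to the study treatment, shall be recorded", so the event is captured, but as a non-serious AE.
- *Outcome.* Section 5.3.5 has a category for resolution with sequelae, and Form 8 asks for a description of them. Neither changes seriousness or triggers a 24-hour report.
- *Severity.* Section 5.3.1 grades discomfort and interference with activity, so a painless permanent scar could be graded mild.
- *Unanticipated device effects.* These share the 24-hour limit in 5.5, and scarring is not in the anticipated list in 5.4.2. But the supplied text does not define the term, and Form 8 asks only whether the event was an unanticipated adverse event. This route is possible but cannot be confirmed.

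**Step 4: scale.** Section 7.2 gives 15 subjects. With all 15 treated, one reclassified subject changes the SAE percentage by 1/15 = 0.067, or 6.7 percentage points (for example 1/15 against 0/15). Section 2.2 says up to 15, so with fewer treated the step 1/n would be larger. This shows the size of one event, not how likely one is.

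**Step 5: effect of the correction.** With structure added to the impairment item, the test case meets that item and becomes an SAE. A minor mark that is not a serious deterioration in health is not an SAE before or after the change.

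**The case against.** The case for leaving the text alone has real weight, and much of it limits the point.

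- **A reader might infer that any untreated scar escapes the definition.** The documents do not support that. A scar with permanent functional loss can meet the function item without treatment.
- **A reader might call the list self-contradictory.** It is not. No two items give opposite answers for the same event; one kind of event is simply not covered.
- **Serious deterioration is required throughout.** Intervention to prevent structural damage does not make an event serious by itself, and a peripheral corneal scar that spares vision might be judged not serious even after the correction. This stands: the change matters only for events that pass that condition.
- **Permanent loss of meibomian glands might seem an obvious example.** Section 1 describes these glands by what they secrete, so losing them is arguably functional impairment and already covered.
- **The case with no intervention is narrow.** Section 5.3 has the investigator take necessary therapeutic measures, so many injuries would fall under the intervention item. An injury judged not to need treatment, or recognised only once permanent, would not.
- **Little suggests that such events are likely.** Section 5.4.2 anticipates pain, irritation, inflammation and ocular symptoms. Section 5.4.1 reports no adverse events in 30 earlier subjects and no adverse histological findings in rabbits. This bears on probability, not on whether the definition is complete.
- **No decision rule turns on the SAE count.** Section 7 tests no hypothesis, and the safety reason for termination in section 6 refers to the incidence or severity of adverse events. This also stands.

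**Conclusion.** The point holds in a narrow form. Under 5.2 and Form 8, an event that causes serious deterioration in health and permanent structural damage, without permanent functional loss, intervention or any other criterion, is not an SAE. Intervention to prevent the same damage could make the event one.

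The consequence is limited to classification, the SAE tabulation and the 24-hour duty that follows from SAE status. A reader might infer that the event would go unrecorded or unreported. The documents do not support that: it stays an AE, its sequelae can be described, and it might be reported as an unanticipated adverse device effect. Those provisions reduce the effect but do not reliably restore SAE status or prompt reporting.

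The 6.7 points is scale only and assumes 15 treated subjects. The sample size and the temperature summaries are unaffected. The conclusion rests on the list being applied as worded and on no wider definition standing in text that was not supplied.

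**What to change.** In section 5.2 and on Form 8, insert the four words *structure or a body* before *function* in the permanent-impairment item, so that it covers the same ground as the intervention item. Keep the introductory condition of serious deterioration in health, so that trivial marks do not become SAEs.

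The cost is four words in two places, using terms already in the sponsor's list. It needs no extra data, assessments or subjects, and no change to the analysis.

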5.3 ADVERSE EVENT ASSESSMENT AND DOCUMENTATION

All subjects who have been exposed to the study treatment shall be evaluated for adverse events. All adverse events, regardless of severity and whether or not they are ascribed to the study treatment, shall be recorded in the source documents and CRF using standard medical terminology.

All adverse events shall be evaluated beginning with onset, and evaluation shall continue until resolution is noted, or until the investigator determines that the subject's condition is stable. The investigator shall take appropriate and necessary therapeutic measures required for resolution of the adverse event. Any medication necessary for the treatment of an adverse event must be recorded on the adverse event case report form.

All AEs shall be characterized by the following criteria:

Page 32 of 65

- Event diagnosis
- Intensity or severity
- Expectedness
- Relatedness to study treatment
- Treatment or action taken.
- Outcome

Whenever possible, recognized medical terms should be used when recording AEs. Colloquialisms and/or abbreviations should not be used. Only one medical concept, preferably a diagnosis instead of individual symptoms, shall be recorded as the event.

If more than one distinct adverse event occurs, each event shall be recorded separately.

5.3.1 Classification of Adverse Events by Intensity/Severity

All adverse events shall be graded on a three-point scale (mild, moderate, severe) for intensity/severity, defined as a qualitative assessment of the level of discomfort of an adverse event as is determined by the Investigator or reported to him/her by the subject. The assessment of intensity is made irrespective of study procedure relationship or seriousness of the event and shall be evaluated according to the following scale:

Mild: Awareness of sign or symptom, but easily tolerated.

Moderate: Discomfort enough to cause interference with usual activity.

Severe: Incapacitating with inability to work or do usual activity.

There is a distinction between the severity and the seriousness of an adverse event. Severity is a measurement of intensity; thus, a severe reaction is not necessarily a SAE.

5.3.2 Expectedness

All AEs shall be evaluated as to whether they are expected or unexpected.

Expected (anticipated): An adverse event is expected when the nature,

severity, or degree of incidence was previously described, including those events listed in section

5.4.2.

Unexpected (unanticipated): An adverse event is unexpected when the nature,

severity, or degree of incidence was not

previously described.

5.3.3 Relatedness

The study investigator shall evaluate if the AE is related to the iLux heating. Relationship is defined in the following manner:

Not related: The event is clearly related to other factors such as subject's

clinical state, therapeutic interventions, concomitant disease or therapy administered to the subject, and does not follow a

known response pattern to the procedure.

Related:

The event follows a reasonable, temporal sequence from the time of procedure and/or follows a known response pattern to the study procedure and cannot be reasonably explained by other factors such as subject's clinical state, therapeutic interventions, or concomitant therapy administered to the subject.

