1.1 INDICATION FOR USE

The iLux System is indicated for the application of localized heat and pressure therapy in adult patients with chronic cystic conditions of the eyelids, including meibomian gland dysfunction (MGD), also known as evaporative dry eye.

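### Do the relatedness definitions in section 5.3.3 and the two attribution questions on Form 8 need rewriting?

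*Combined protocol and SAP*

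**What the plan says.** Section 5.3 lists the items to be recorded for each adverse event, among them "Relatedness to study treatment". Section 5.3.3 puts the question as "The study investigator shall evaluate if the AE is related to the iLux heating" and then gives two classes, both worded for the procedure:

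- **Not related:** "The event is clearly related to other factors such as" the subject's clinical state or other therapy, and in addition the event does not fit a known response to the procedure.
- **Related:** the timing is reasonable and/or the event "follows a known response pattern to the study procedure", and it "cannot be reasonably explained by other factors such as" the same list of alternatives.

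Form 8 (Appendix 2: Case Report Forms) has two items, "Was the event device-related" and "Was the event procedure-related", each with a Related and a Not Related box and nothing else.

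Section 7.3 summarises adverse events by the number and percentage of subjects with each one. It does not mention relatedness.

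**The concern.** Two things look wrong.

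First, the object of attribution shifts between study treatment, heating, procedure and device. Section 1.1 describes the device as meant for "application of localized heat and pressure therapy", and section 5.4.1 accepts that the disposable may touch the ocular surface. Pain from compression, or irritation from contact, is not an effect of heat. It can still be an effect of the procedure and, in ordinary language, of the device. A reaction to the anesthetic drops belongs to the procedure but not to the device. One set of criteria cannot obviously answer both Form 8 items.

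Second, the two classes are not complements, so some events meet neither definition while the form requires a box to be ticked.

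The stake would be the safety reading. Section 7.2 describes the sample as serving an initial safety assessment, the trial is open label and non-randomized, and both eyes are treated. With no control arm or untreated eye, attribution rests on judgment, and unclear criteria could make that judgment hard to reproduce.

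**Working it through.** **Are the classes complementary?** The plan gives no figure to reproduce, so the check is a truth table on the attributes named in 5.3.3: timing fits (yes/no), known pattern (yes/no), other cause (none / reasonable but not clear / clear). That gives 2 × 2 × 3 = 12 combinations.

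Reading A, the plain one: Related = (timing or pattern) and no other cause; Not related = clear other cause and no pattern.

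| Timing | Pattern | Other cause: none | Reasonable | Clear |
|---|---|---|---|---|
| yes | yes | Related | no class | no class |
| yes | no | Related | no class | Not related |
| no | yes | Related | no class | no class |
| no | no | no class | no class | Not related |

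Counts: 3 Related, 2 Not related, 12 − 3 − 2 = 7 without a class.

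Reading B attaches the other-cause clause to the pattern limb only: Related = timing or (pattern and no other cause). All 6 rows with fitting timing become Related, plus 1 with pattern alone. One of these (timing, no pattern, clear other cause) is also Not related. Counts: 6 Related only, 1 both, 1 Not related only, 4 without a class; 6 + 1 + 1 + 4 = 12.

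So the classes are not complementary on either reading. The cells are logical combinations without weights and say nothing about how often such events occur.

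**Do the terms really conflict?** Only in part. Appendix 1 uses iLux heating as the single row for the whole treatment, with no separate row for compression or contact. Section 3, on study treatments, opens in 3.1 by saying that the iLux procedure is to be performed. Heating, study treatment and procedure can therefore be read as labels for one activity, and both definitions in 5.3.3 say procedure in any case. What remains is that device-related has no criteria of its own in the visible text. The user manual's text was not available to check.

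**Where does the relatedness entry go next?**

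| Use | Rule in the plan | Depends on relatedness? |
|---|---|---|
| Recording of events | 5.3: all events, whether or not ascribed to treatment | No |
| Event table | 7.3: subjects with each event | No |
| Serious events | 5.5: reported within 24 hours | No |
| Unanticipated device effects | 5.5: same time limit, term not defined in the visible text | Possibly |
| Termination | 6: incidence or severity of events | Not as written |
| Primary endpoint | 7.1: temperature after heating | No |

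**Is Form 8 attribution the only evidence?** No. Form 8 also takes diagnosis, onset time and a narrative. Form 6 records heating time, force and maximum temperature by zone and eye. Form 4 gives slit-lamp, lid and staining findings before and after treatment. Form 9 asks whether a device event led to an adverse event.

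**Would the obvious rewrite be better?** Suppose every event not clearly due to something else is called Related. The classes become exhaustive: 2 × 2 = 4 Not related and 12 − 4 = 8 Related. But 2 of those 8 have neither fitting timing nor a known pattern. Irritation that might come from either the drops or device contact would be Related on both boxes, so the two would still not be separated. If procedure were limited to the listed iLux steps, irritation clearly due to tonometry or fluorescein would fall outside both boxes, although section 5.1 counts events after any protocol-imposed intervention.

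**The case for a change.** The best argument for a change is that this is a safety study without a control, the rewording costs almost nothing, and eyelid or eye pain heads the anticipated events in 5.4.2, so an ambiguous case is not remote. Section 5.5 adds weight. It requires unanticipated adverse device effects to be reported within 24 hours, the visible text does not define them, and Form 8 asks only whether an event was unanticipated. The undefined device item is then the natural way to identify such effects.

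Much of this is fair. The definitions do leave gaps, and two investigators could tick different boxes for the same event. The 5.5 point also stands, but within limits. A serious event is reported anyway, so attribution could decide the matter only for a non-serious, unexpected event, and only if the sponsor reads the term to include such events. That concerns reporting practice and can be settled at the initiation visit, where section 9 has the site trained on carrying out the protocol. It does not affect any estimate or summary.

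**Conclusion.** The observation is correct but has no analytic consequence. Relatedness enters none of the summaries in section 7, so the change in planned output is zero. A table of device-related events would be an addition that the plan does not promise. In it, moving one subject between classes would shift a percentage by 1/15 = 6.7 points, in a direction that cannot be predicted.

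The gap is one that an investigator and analyst fill sensibly: apply the criteria to each Form 8 item in turn, treat an event with fitting timing or pattern and no clear other cause as related, and describe doubtful cases from the narrative. With at most 15 subjects at one centre, that is practicable.

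This rests on three assumptions: that section 7.3 is followed as written, that the text not available for review does not make relatedness an input to an analysis, and that doubtful unanticipated events are raised with the sponsor under 5.5.
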